3.3 Inclusion of Women and Minorities

Both men and women of all races and ethnic groups are eligible for this trial.

4. REGISTRATION AND RANDOMIZATION PROCEDURES

4.1 General Guidelines for DF/HCC Institutions

Institutions will register eligible participants in the Clinical Trials Management System (CTMS) OnCore. Registrations must occur prior to the initiation of any protocol-specific therapy or intervention. Any participant not registered to the protocol before protocol-specific therapy or

intervention begins will be considered ineligible and registration will be denied.

An investigator will confirm eligibility criteria and a member of the study team will complete the protocol-specific eligibility checklist.

The eligibility checklist and all pages of the consent form will be faxed to the DF/HCC Office of Data Quality (ODQ) at [contact]. The ODQ will (a) review the eligibility checklist, (b) register the participant on the protocol, and (c) when applicable, randomize the participant.

Randomization can only occur during ODQ business hours (8:30am – 5pm Eastern Time, Monday through Friday excluding holidays).

An email confirmation of the registration and/or randomization will be sent to the PI, study coordinator(s) from the registering site, treating investigator and registering person immediately following the registration and/or randomization.

As this is a double-blinded study in the randomized portion (Part II), an email confirmation of the treatment assignment (troriluzole vs. placebo) will be sent to the investigational pharmacy team.

Following registration, participants may begin protocol-specific therapy and/or intervention. Issues that would cause treatment delays should be discussed with the Principal Investigator (PI) of the registering site. If the subject does not receive protocol therapy following registration, the subject must be taken off study in the CTMS (OnCore) with an appropriate date and reason entered.

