5.10 Criteria for Taking a Participant Off Study

Safety Run-In and Randomized Treatment:

Participants will be removed from study (including study follow-up) when any of the following criteria apply:

- Lost to follow-up
- Withdrawal of consent for data submission
- Death

The reason for taking a participant off study, and the date the participant was removed, must be documented in the case report form (CRF). In addition, the study team will ensure the participant's status is updated in OnCore in accordance with [REGIST-OP-1](#).

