11.5 Progression-Free Survival

Progression-Free Survival: Progression-Free Survival (PFS) is defined as the time from randomization (or registration) to the earlier of progression in the intracranial or extracranial sites or death due to any cause. Herein, the term “PFS” refers to PFS in both the intracranial and extracranial compartments (global). The follow-up of participants alive without disease progression is censored at date of last disease evaluation.

Time to Progression: Time to Progression (TTP) is defined as the time from randomization (or registration) to progression, or censored at date of last disease evaluation for those without progression reported.

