Following the Safety Run-in, all participants will be enrolled on the randomized portion of the study.

Primary Endpoint. The primary endpoint of the study is global progression-free survival in patients with melanoma brain metastases who are treated with INT vs. INP. Of particular interest will be PFS at 6 months.

PFS is defined as the time from random assignment to the earlier of death or documented disease progression in the intracranial or extracranial compartments. The follow-up of patients who have neither died nor progressed will be censored at the date of the last follow-up visit.

Secondary Endpoints. The secondary objectives and their associated endpoints evaluate other important clinical outcomes, including overall survival (OS), intracranial response rate (RR) and

PFS, extracranial RR and PFS, and safety (number of participants experiencing adverse events, particularly neurologic events). We will also investigate:

- tolerability (number of induction cycles administered, number of maintenance cycles administered)
- use of corticosteroids for management of symptomatic cerebral edema (number of participants)
- use of corticosteroids for management of immune related adverse events (number of participants who require prednisone ≥ 1 mg/kg or equivalent)
- frequency of clinically-indicated stereotactic radiation therapy to the brain on study (number of patients, number of instances and number of lesions irradiated)
- frequency of clinically-indicated surgical intervention to the brain on study (number of participants)

Planned subgroup analyses according to baseline characteristics:

- Prior anti-PD-1 exposure (yes vs. no – if yes then adjuvant vs. metastatic setting)
- Prior ipilimumab exposure (yes vs. no)
- Age (<65 years vs 65 years or older)
- ECOG (0 vs 1)
- LDH at baseline (normal vs. elevated)
- Number of brain metastases (<3 vs 3 or more)
- Brain-directed stereotactic radiation therapy prior to study entry (yes vs. no)
- Craniotomy prior to study entry (yes vs. no)

Planned subgroup analyses according to on-study events:

- On-study brain-directed stereotactic radiation therapy (yes vs. no)

Exploratory Endpoints:

- associations between BRAF/NRAS mutation status and response endpoints, as well as tissue biomarker profiles between paired tissues from extracranial and intracranial metastases from individual patients, where available

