13.6 Analysis of Secondary Endpoints

Overall Survival

Overall Survival (OS) is defined as the time from randomization (or registration) to death due to

any cause, or censored at date last known alive. Estimates of overall survival will also be from a PHMC model (Section 13.5). Long-term survival estimates and comparisons will be based on the incidence portion of the model; hazards of death will be based on the latency portion of the model. The distribution of deaths will be summarized using marginal survival function curves.

Intracranial or Extracranial Response

The proportion of patients in each treatment arm with intracranial response (RECIST) will be presented with exact, 90% binomial confidence intervals. The randomized treatment arms will be compared using Fisher's exact test. Comparable comparisons will be conducted for extracranial response (RECIST).

Intracranial or Extracranial PFS

Extracranial PFS is defined as the time from first dose of study therapy to documented extracranial progression (per RECIST) or death, whichever occurs first. Intracranial PFS is defined as the time from first dose of study therapy to documented intracranial progression or death, whichever occurs first. For both endpoints, the follow-up of patients who have neither died nor progressed at the time of analysis will be censored at the date of last adequate disease assessment. Treatment comparisons of intracranial or extracranial PFS will be based on PHMC methods outlined in Section 13.5. Point estimates at 6 months will be presented with confidence intervals.

Safety Data

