13.7 Reporting and Exclusions

Evaluation of Toxicity

All participants will be evaluable for toxicity from the time of their first treatment.

Evaluation of the Primary Efficacy Endpoint

The analysis of the primary endpoint will be conducted using the intention-to-treat principal, meaning all randomized patients will be evaluated according to the treatment assigned at the time of enrollment.

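### Randomized patients who never start therapy are to be taken off study with no stated follow-up, although the primary analysis is meant to include everyone randomized

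*Combined protocol and SAP*

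**What the plan says.** - **Registration and randomization.** Under Section 4.1 the data quality office will "register the participant on the protocol, and (c) when applicable, randomize the participant". Both steps come before any protocol therapy. Appendix B, Section 3.5, likewise returns the assigned treatment to an external site once registration is confirmed.
- **Non-starters.** Section 4.1 continues: "If the subject does not receive protocol therapy following registration, the subject must be taken off study in the CTMS (OnCore", with a date and a reason. Section 4.3 has the same rule for external sites, where up to 10 days are allowed between registration and first treatment. Neither section exempts Part II.
- **Meaning of off study.** Off protocol therapy (Section 5.8) and off study (Section 5.10) are separate states. Section 5.10 opens: "Participants will be removed from study (including study follow-up) when any of the following criteria apply". It then lists three criteria: loss to follow-up, withdrawal of consent for data submission, and death. Failure to start is not among them.
- **Primary analysis.** Section 13.7 adopts intention to treat, "meaning all randomized patients will be evaluated according to the treatment assigned at the time of enrollment".
- **Censoring.** For PFS, Section 11.5 says: "The follow-up of participants alive without disease progression is censored at date of last disease evaluation". Section 13.1 says: "The follow-up of patients who have neither died nor progressed will be censored at the date of the last follow-up visit". For overall survival, Section 13.6 runs to death "or censored at date last known alive".

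**The concern.** The registration rule and the analysis population pull in opposite directions. Section 13.7 counts every randomized patient, but Sections 4.1 and 4.3 remove some of them before any post-baseline assessment, and no section arranges to observe them afterwards. The early-discontinuation visits in Section 10 (footnote i) are for patients who stop treatment early, which does not describe someone who never began.

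The plan itself creates a route to non-starting. Section 5.2 requires all eligibility criteria to be met again on Day 1. These include performance status, organ function and no need for immediate local brain treatment. A patient who deteriorates between randomization and Day 1 may therefore not start. If such patients do worse than the rest, losing their outcomes makes absolute PFS and survival look better than they are. The 6-month PFS proportion, which Section 1.2 singles out, is the estimate most directly exposed.

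**Working it through.** **1. What a non-starter contributes.** PFS runs from randomization. A never-treated patient who is alive and progression-free when taken off study has only the baseline scan, so Section 11.5 censors at or before time zero. Section 13.1 has no follow-up visit to use. In a mixture cure model with uncured probability π and latency survival S(t), a patient censored at t contributes (1 − π) + πS(t). At t = 0, S = 1 and the contribution is 1, whatever the parameters. The patient carries no information.

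**2. Events implied by the design.** The protocol gives no final event count. Inputs from Section 13.2: 45 per arm, accrual 24 months, further follow-up 12 months, control 6-month PFS 0.6, cured fractions 0.30 and 0.50, hazard ratio 0.557.

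- Control latency hazard: λ0 = −ln[(0.6 − 0.3)/0.7]/6 = 0.1412 per month.
- INT latency hazard: λ1 = 0.557 × 0.1412 = 0.0787 per month.
- Events per arm = 45 × (1 − cured) × {1 − [exp(−12λ) − exp(−36λ)]/(24λ)}.
- INP: 45 × 0.70 × (1 − 0.0524) = 29.9.
- INT: 45 × 0.50 × (1 − 0.1749) = 18.6.
- Total: about 48.4.

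**3. Share of events at risk.** Assume 2-5% do not start.

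- 2% of 90 = 1.8, and 1.8/48.4 = 3.7%.
- 5% of 90 = 4.5, and 4.5/48.4 = 9.3%.

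These are upper limits, because they treat every non-starter as a lost event. (Five whole patients would be 5/48.4 = 10.3%.) If non-starters had average outcomes, removing five takes expected events from 48.4 to 45.7, a loss of 2.7/48.4 = 5.6%.

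**4. Power.** The plan's figure comes first. Section 13.2 claims 80% at type-I error 0.1, without saying one- or two-sided. A numerical log-rank calculation under the same cure model, two-sided, with INT 6-month PFS of exactly 0.8 (latency hazard ratio 0.603) gives 80.4% at N = 90; a local-alternative formula gives N = 89. The plan's figure is thus reproduced. The printed hazard ratio 0.557 implies INT 6-month PFS 0.812 and gives 83.7%. The package cited in the plan was not available for the check.

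The standardized effect scales with √N. For 80.4% it is 0.854 + 1.645 = 2.499. With five patients contributing nothing it becomes 2.499 × √(85/90) = 2.429, and power is Φ(2.429 − 1.645) = 78.3%.

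| Non-starters of 90 (assumed) | Power, HR 0.603 | Power, HR 0.557 |
|---|---|---|
| 0 | 80.4% | 83.7% |
| 2 | 79.6% | 83.0% |
| 5 | 78.3% | 81.8% |
| 9 | 76.6% | 80.2% |

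**5. Range for 6-month PFS in one arm.** Suppose 3 of 45 are unobserved and the other 42 show 0.60.

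- All three fail: 42 × 0.60/45 = 0.56.
- None fails: (42 × 0.60 + 3)/45 = 0.63.
- If the 42 show 0.80, the same limits are 0.75 and 0.81.

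**The case against.** The strongest reply is that Section 4.1 asks only for a status entry in the trial management system and never says that data collection stops. The words about follow-up stand in Section 5.10, attached to three criteria that do not include non-start. The registration policy cited in Section 4.2 might settle the meaning, but it is not in the documents. This is fair, and it makes the problem one of conflicting sections rather than a proven stop to follow-up. It does not remove the problem: even on the lenient reading, no section provides follow-up for a randomized patient who was never treated.

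Three stronger readings may tempt a reader, and the documents do not support them.

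- *These patients have no outcome data at all.* A death or progression before the off-study date can still be recorded. The gap begins at that date.
- *The trial becomes an as-treated analysis.* Nobody is moved to another arm. The result is closer to a modified intention-to-treat analysis of treated patients.
- *The comparison is biased towards troriluzole.* Part II is double-blind, assignments go to the pharmacy, and both arms receive ipilimumab and nivolumab. Non-start before the first dose is therefore unlikely to depend systematically on arm. Chance imbalance remains possible with 45 per arm.

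It is also true that Section 13.7 makes its commitment for the primary endpoint only, so lost survival data are a weakness but not a contradiction of that section. Nor do the documents say that non-starters have the worst prognosis; logistics or withdrawal are other possible reasons.

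**Conclusion.** The point holds as an unreconciled conflict between Sections 4.1 and 4.3, Section 5.10 and Section 13.7. Followed as written, it leaves randomized non-starters in the intention-to-treat set in name only.

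The effect is small and its size rests on an assumed non-start rate of 2-5%, for which the documents give no basis. On that assumption, at most about 4-9% of the roughly 48 model-implied events are at risk, and about 2 points of power at five patients. The main harm is possibly optimistic absolute PFS and survival, if non-starters fare worse than others. Between-arm bias is possible mainly through chance imbalance. This is a minor point, worth correcting because the missing outcomes may not be recoverable later.

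**What to change.** - **Sections 4.1 and 4.3:** limit the off-study rule to the safety run-in. For Part II, state that a randomized patient who does not start is recorded as off protocol therapy, with date and reason, and stays in follow-up for progression and survival unless consent is withdrawn.
- **Data sources:** collect survival through the 12-weekly phone contact or chart access already in Section 5.9. Phone contact will not supply progression, so capture that on case report forms from study or standard-of-care scans, as Section 5.9 already does for later follow-up.
- **Section 5.10:** make it consistent, so that failure to start does not end study follow-up in Part II.

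The cost is a few sentences and the follow-up of a few extra patients. Their progression dates may fall off the study scan schedule. The change does not bring these patients into the intracranial and extracranial PFS endpoints: Section 13.6 starts both clocks at first dose, which a never-treated patient does not have.

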4.2 Registration Process for DF/HCC Institutions

Applicable DF/HCC policy (REGIST-101) must be followed.

4.3 General Guidelines for Other Investigative Sites

Eligible participants will be entered on study centrally at DF/HCC by the Study Coordinator. All sites should contact the Study Coordinator at DFC to verify slot availability:
[contact]

The required form, the External Site Subject Registration Form, can be found in Appendix E.

Following registration, participants should begin protocol therapy within 10 days. Issues that would cause treatment delays should be discussed with the Sponsor-Investigator. If the subject does not receive protocol therapy following registration, the subject must be taken off study in the CTMS (OnCore) with an appropriate date and reason entered.

4.4 Registration Process for Other Investigative Sites

To register a participant, the following documents should be completed by the participating site and faxed ([contact]) or e-mailed ([contact]) to the Study Coordinator at DFCI:

- Copy of brain MRI
- Signed participant consent form
- HIPAA authorization form (if not included in consent form)
- Eligibility Checklist
- External Site Subject Registration Form (Appendix E)

The participating site will then contact the Study Coordinator at DFCI ([contact]) to verify eligibility. The Study Coordinator will follow DF/HCC policy (REGIST-101) and register the participant on the protocol. The Study Coordinator will fax or e-mail the participant study number to the participating site. The Study Coordinator will also contact the participating site and confirm registration.

5. TREATMENT PLAN

5.1 Treatment Regimen

Cycle length is variable during this protocol. During the induction phase, cycles are 3 weeks. During the maintenance phase, cycles are 4 weeks.

5.1.1 Safety Run-In:

The starting dose of the Safety Run-In is outlined below. Up to three cohorts of participants will be treated in a 3+3 design. At the end of each cohort accrual of 3 participants, enrollment will pause for a comprehensive review of the safety data including dose-limiting toxicity (DLT). A starting dose of Troriluzole at 140 mg/280 mg will be used. If there are ≥ 2 DLTs as defined in Section 6.2, the fallback dose in cohort -1 will be used for three new participants accrued to Cohort -1. If there are < 2 DLTs in the first three participants, an additional three participants will be added to the starting cohort. From this point, if fewer than two patients within a cohort have DLTs then that dose level will be considered the MTD and enrollment to the randomized trial will begin. If two or more patients within a safety cohort have DLTs, then the dose will either be de-escalated, or the trial will stop. A participant will be considered to have completed the DLT period with no dose limiting toxicities only if they have taken $\geq 80\%$ of their assigned Troriluzole doses in the DLT period, which is the first 6 weeks of treatment.

Table 5.11 Cohort de-escalation table during safety run-in:

Dose Level	Troriluzole Dose
Starting cohort	140 mg PO QAM and 280 mg PO QPM
Cohort -1	140 mg PO BID

Cohort -2	140 mg PO daily
If ≥ 2 DLTs on Cohort -2	Permanently stop the trial

During the induction phase:

Nivolumab (1 mg/kg) followed by ipilimumab (3 mg/kg) will be administered every 3 weeks, with 21 consecutive days defined as a treatment cycle. Troriluzole will be continuously self-administered orally twice a day (at the dose level indicated by participant's cohort).

During the maintenance phase:

Nivolumab (480 mg IV) will be administered every 4 weeks, with 28 consecutive days defined as a treatment cycle. Troriluzole will be continuously self-administered orally twice a day (at the dose level indicated by participant's cohort).

Treatment will be administered on an outpatient basis. Reported adverse events and potential risks are described in Section 7. Appropriate dose modifications are described in Section 6. No investigational or commercial agents or therapies other than those described below may be administered with the intent to treat the participant's malignancy.

Table 5.12

Regimen Description – Induction					
Agent	Premedications; Precautions	Dose	Route	Schedule	Cycle Length
Troriluzole	Take with or without food.	Twice daily per cohort assigned dose	Oral, 140 mg capsules	Days 1-21*	3 weeks
Nivolumab		1 mg/kg over 30 minutes**	IV	Day 1	
Ipilimumab		3 mg/kg over 30 minutes**	IV 0-60 min after completion of nivolumab through separate IV line	Day 1	

*The participant will be requested to maintain a medication diary of each dose of medication. The medication diary will be returned to clinic staff at the end of each cycle
 
** Infusion time windows of -5 min/+ 10 min are allowed
					

Regimen Description – Maintenance					
Agent	Premedications; Precautions	Dose	Route	Schedule	Cycle Length

Troriluzole or placebo	Take with or without food.	Twice daily per cohort assigned dose	Oral, 140 mg capsules	Days 1-28*	4 weeks
Nivolumab		480 mg over 30 minutes**	IV	Day 1	

*The participant will be requested to maintain a medication diary of each dose of medication. The medication diary will be returned to clinic staff at the end of each cycle
 
** Infusion time windows of -5 min/+ 10 min are allowed
					

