5.3 Agent Administration

Safety Run-In and Randomized Treatment:

Administration and Dosing. As nivolumab and ipilimumab are FDA approved for metastatic melanoma, administration will follow institutional standard/package insert. The IV agents are not vesicants or irritants. No observation period is necessary. Doses of nivolumab and ipilimumab are weight-based during the induction phase. It is acceptable to use baseline weight for all induction cycles. In the instance that the institutional policy is more strict, institutional policy should be followed. Refer to table in Section 5.1. Details are provided below for reference.

During the induction phase:

Nivolumab (1 mg/kg) followed by ipilimumab (3 mg/kg) 0-60 minutes later will be administered every 3 weeks, with 21 consecutive days defined as a treatment cycle. Troriluzole vs. placebo will be continuously self-administered orally twice a day (140 mg PO QAM and 280mg PO QPM; or twice daily per cohort assigned dose if in Safety Run-In). Due to toxicity, not all patients are expected to complete all 4 cycles of the induction. See section 6 for dosing modifications/omissions.

During the maintenance phase:

Nivolumab (480 mg IV) will be administered every 4 weeks, with 28 consecutive days defined as a treatment cycle. Troriluzole vs. placebo will be continuously self-administered orally twice a day (140 mg PO QAM and 280mg PO QPM; or twice daily per cohort assigned dose if in Safety Run-In).

Oral agents, troriluzole vs. placebo. Troriluzole or placebo in a blinded fashion will be self-administered orally with BID dosing Q 12 hours (\pm 2 hours). On a continuous basis throughout the protocol. Capsules can be taken with or without food; if a patient experiences nausea, taking the capsule with food is recommended. Capsules cannot be crushed, chewed, or dissolved. If a dose has been missed or it is vomited up, it should be skipped. Patients may choose to use an antiemetic prior to taking troriluzole if needed.

Order of administration: On Cycle 1 Day 1, the nivolumab will be administered first, followed by the ipilimumab, and in the evening, the first dose of troriluzole or placebo will be self-administered at home. For subsequent cycles, troriluzole or placebo will be self-administered in the morning before coming to the outpatient infusion center, followed by the infusion(s), and then troriluzole will be self-administered in the evening.

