Qualified personnel, familiar with procedures that minimize undue exposure to themselves and the environment, should undertake the preparation, handling, and safe disposal of the chemotherapeutic agent in a self-contained and protective environment.

Availability

The investigational drug and placebo will be supplied by Biohaven Pharmaceuticals. The drug substance is manufactured and purchased commercially from Anthem Biosciences.

Preparation

N/A

Administration

Troriluzole or placebo will be self-administered by the patient orally with continuous BID dosing. Ideally, BID dosing will be as close to Q 12 hours (± 2 hours) apart as possible (minimum 10 hours apart). Troiriluzole may be taken either with food or on an empty stomach.

Ordering

Each site will order drug from Biohaven Pharmaceuticals using the form provided. Drug should be ordered at least 7 days in advance of anticipated dispensing.

Accountability

The investigator, or a responsible party designated by the investigator, should maintain a careful record of the inventory and disposition of the agent using the NCI Drug Accountability Record Form (DARF) or another comparable drug accountability form. (See the NCI Investigator's Handbook for Procedures for Drug Accountability and Storage.)

Destruction

Expired, empty and partially empty containers of study drug will be disposed of/destroyed in accordance with institutional policies and procedures. Unused containers of study drug will not be returned to the study sponsor.

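### The general dosing text gives troriluzole twice daily without exception, but the lowest dose level is listed as 140 mg daily, and with a 140 mg capsule both cannot be followed

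*Combined protocol and SAP*

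**What the plan says.** The general regimen text gives troriluzole twice daily in five places:

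- Section 5.1.1, induction and maintenance: "Troriluzole will be continuously self-administered orally twice a day (at the dose level indicated by participant's cohort".
- Table 5.12, both phases: "Twice daily per cohort assigned dose", supplied as 140 mg capsules.
- Section 5.3, which covers the run-in and the randomized part: "or twice daily per cohort assigned dose if in Safety Run-In", and then "self-administered orally with BID dosing Q 12 hours". Its paragraph on order of administration describes a morning and an evening dose.
- Section 8.1: "Troriluzole or placebo will be self-administered by the patient orally with continuous BID dosing".
- The study calendar in Section 10, whose troriluzole row is labelled as twice-daily dosing.

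Three tables define the dose levels: Table 5.11, the reduction table in Section 6.3 and the cohort table in Section 13.1. Each lists 140 mg in the morning plus 280 mg in the evening, then 140 mg BID, then "140 mg PO daily".

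The only strength described (Table 5.12, Section 8.1) is a 140 mg capsule, and Section 5.3 does not allow capsules to be broken up before swallowing.

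**The concern.** The lowest level is used only after toxicity: for a new cohort when Cohort -1 has produced two or more DLTs, or for an individual participant after dose reductions under Section 6.3. In the tables it differs from the level above only in frequency, and frequency is what the general text states differently. If a site took the amount from the table and the frequency from the text, the last step down would leave the dose unchanged.

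Two things would be at stake. In the run-in, the rule that ends the trial after two or more DLTs on Cohort -2 could be decided on participants taking the Cohort -1 dose. In either part, a participant moved from level -1 to level -2 might have no reduction in exposure. The adherence rules are also affected, because the number of assigned doses at the lowest level depends on which frequency is used.

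**Working it through.** **Inputs.** Capsule strength 140 mg (Table 5.12, Section 8.1). Whole capsules only (Section 5.3). Three dose levels (Table 5.11 and the tables in 6.3 and 13.1). DLT period of 6 weeks, or 42 days, with at least 80% of assigned doses taken (5.1.1, 13.1). Desired compliance above 75% (5.3).

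**Daily dose according to the tables.** Daily dose = sum of the day's administrations.

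- Starting cohort / level 0: 140 + 280 = 420 mg (3 capsules).
- Cohort -1 / level -1: 140 + 140 = 280 mg (2 capsules).
- Cohort -2 / level -2: 140 mg (1 capsule), reading daily as once a day. The tables do not say once daily, but the contrast with BID one row above makes that the natural reading.

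**Lowest level if the twice-daily wording is applied to it.** There are two ways to read the wording:

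- 140 mg at each administration: 2 x 140 = 280 mg/day. This equals Cohort -1 / level -1 and is twice the table figure (280 / 140 = 2).
- 140 mg/day split over two administrations: 140 / 2 = 70 mg each, or 70 / 140 = half a capsule. The product described cannot give this.

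Neither reading gives the table entry with whole capsules. On the first, the sequence 420 / 280 / 140 mg/day becomes 420 / 280 / 280.

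**Effect on the Section 6.3 reductions, on that first reading.**

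- Level -1 to level -2: 280 to 280 mg/day, no reduction.
- Two levels from level 0 (required if drug is resumed after a grade 4 event): 420 to 280 mg/day. The dose falls, but only as far as with the one-level reduction required after a grade 3 event.

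**Effect on dose counts over 42 days.**

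- Once daily: 42 doses; 0.8 x 42 = 33.6, so at least 34.
- Twice daily: 2 x 42 = 84 doses; 0.8 x 84 = 67.2, so at least 68.
- A fully adherent once-daily participant counted against a twice-daily schedule: 42 / 84 = 50%, below both 80% and 75%.

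These counts take 42 full days. Section 5.3 starts troriluzole on the evening of Day 1, which would remove one twice-daily administration (83 doses; 0.8 x 83 = 66.4, so at least 67). The conclusion does not change.

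**The case against.** The strongest reply is that the run-in wording names no amount of its own. It sends the reader to the cohort's assigned dose, and Table 5.11 gives amount and frequency together. To reach 280 mg/day, a site would have to take the amount from the Cohort -2 row, drop that row's frequency, and overlook that frequency is all that separates it from the row above. For individual reductions, Sections 5.1.1 and 5.1.2 refer dose modifications to Section 6, so the specific table can be read as overriding the general text. The 80% rule counts assigned doses, which a careful reader would take from the cohort, and the compliance rule names no twice-daily denominator. The pill diary is a separate document, so its content cannot be judged here.

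Much of this stands. A reader might infer that anyone who follows the text will take the Cohort -1 dose. The documents do not support that, because deferring to the tables is a reasonable reading. Nor do they support the inference that a grade 4 reduction from level 0 is cancelled: even on the adverse reading the dose falls from 420 to 280 mg/day. Table 5.13 is not part of the conflict either. It gives capsule counts for the anticipated MTD, and 5.1.2 undertakes to amend the randomized regimen if the MTD is lowered.

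The reply does not remove the contradiction. The words twice daily remain untrue of the lowest level as tabulated, and the BID statements for the oral agent in 5.3 ("Troriluzole or placebo in a blinded fashion will be self-administered orally with BID dosing Q 12 hours") and in 8.1 carry no reference to cohort. The amendment undertaking in 5.1.2 does not reach participants in Cohort -2 during the run-in or individual reductions to level -2. The calendar footnote allows the dose level to change by cohort but does not mention frequency.

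**Conclusion.** The dosing passages contradict one another at the lowest level, and no whole-capsule schedule satisfies them all. If the twice-daily wording were applied there, the daily dose would be 280 mg against 140 mg in the tables. The step from -1 to -2 would have no effect, and a two-level reduction from level 0 would equal a one-level reduction. This is a possible dosing error, not a certain one, and the documents give no basis for estimating how often it would occur.

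Its reach is conditional. In the run-in it needs both the starting cohort and Cohort -1 to fail, and would then involve the 3 to 6 participants of Cohort -2. Otherwise it concerns participants reduced to level -2, whose number the documents do not project. Alpha, power, sample size and the primary analysis are unaffected. The point still deserves correction because these are operative instructions for a self-administered drug at several sites, and they come into use only after toxicity. The result rests on reading daily as once a day and on 140 mg being the only strength supplied. It does not say which schedule is right.

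**What to change.** Reconcile the twice-daily statements in 5.1.1, Table 5.12, 5.3, 8.1 and the study calendar with Table 5.11 and the tables in 6.3 and 13.1, so that the frequency at the lowest level is stated the same way everywhere. The sponsor must decide which frequency that is. State that assigned doses, for the 80% DLT-period rule and the 75% compliance level, are counted on the reconciled frequency, and check that the pill diary agrees. Table 5.13 needs no change on this ground.

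The cost is a wording amendment to a few sections and, if the check shows it is needed, to the diary. No design parameter or analysis changes.
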